## **Appendix I      European Organization for Research and Treatment of Cancer (EORTC) Quality of Life Questionnaire-Core 30 (QLQ-C30) and PedsQL-Core Module (PedsQL) and Bowel Diary**

### **EORTC QLQ-C30**

The EORTC QLQ-C30 is a questionnaire developed to assess the quality of life of cancer patients. It is a copyrighted instrument, which has been translated and validated in over 100 languages and is used in more than 3,000 studies worldwide. This study is utilizing version 3.0, and the study manual should be consulted for instructions on implementing and scoring.

### **PedsQL™ 4.0 Core Module**

The Pediatric Quality of Life inventory is a modular tool to measure health-related QOL in children and adolescents and validated for patients age 2 to 18 years. The instrument uses child self-reporting as a generic core measure integrated into disease specific modules to provide one assessment.

## Appendix J Examples of Agents Known to Cause QTc Prolongation

QT interval prolongation was reported in patients receiving selpercatinib in clinical trials. Use with caution in patients with such conditions as congenital long QT syndrome or acquired long QT syndrome, or other clinical conditions that predispose to arrhythmias.

Coadministration of medications known to prolong QTc should be avoided if possible.

**Table 11-12 Examples of Agents Known to Cause QTc Prolongation**

Examples of Agents Known to Cause QTc Prolongation	
Amiodarone	ibogaine
Anagrelide	ibutilide
Azithromycin	levofloxacin
Chloroquine	levomepromazine (methotrimeprazine)
Chlorpromazine	levosulpiride
Cilostazol	methadone
Ciprofloxacin	moxifloxacin
Citalopram	ondansetron
Clarithromycin	papaverine HCl (intracoronary)
Cocaine	pentamidine
Disopyramide	pimozide
Dofetilide	procainamide
domperidone	propofol
Donepezil	quinidine
Dronedarone	roxithromycin
Droperidol	sevoflurane
Erythromycin	sotalol
Escitalopram	sulpiride
Flecainide	sultopride
Fluconazole	terlipressin
halofantrine	terodiline
Haloperidol	thioridazine
hydroquinidine, dihydroquinidine	

Note: The above list is not exhaustive. Please refer to [www.crediblemeds.org](http://www.crediblemeds.org) for a current list of agents known to cause QTc prolongation as well as agents with a possible or conditional risk.

## Appendix K Country-Specific Requirements

### Germany

This section describes protocol changes applicable for participants in study sites in Germany.

This table describes the changes and provides a rationale for the changes.

Protocol Section Number and Name	Description of the Change	Brief Rationale
Synopsis, Section 3.6 Phase 2, Section 4.2. Inclusion Criteria for Phase 2, Section 4.3. Exclusion Criteria for Phase 1 and Phase 2	Removed language regarding Cohort 7 and modified schema	Per regulatory feedback
Synopsis, Section 3.6. Phase 2	Phase 2: corrected number of cohorts to “six”	Correction
Section 4.1. Inclusion Criteria for Phase 1	Added inclusion criterion 14 for Germany	
Section 6.4 Removal of Patients from Therapy or Assessment	Added note sites in Germany	
Section 7 Tests and Evaluations, Section 7.3 Cycles 2 and Higher	Updates were made to remove language regarding reduced visit frequency and the use of local healthcare facilities	Per regulatory request
Table 7-1 Schedule of Assessments	Footnote for Cycle 7 and beyond was modified; Note was added for footnote z to exclude Germany; footnote cc was revised to remove telemedicine.	Per regulatory request
Section 8.3. Determination of Sample Size	Added language to justify the increase of sample size	Per regulatory request
Appendix L Provisions for Changes in Study Conduct During Exceptional Circumstances	Appendix L does not apply to Germany	Per regulatory request

The revised text in the following sections show the changes applicable for adult participants at study sites in Germany. Deletions are identified by ~~strikethrough format~~.

### Synopsis

- Cohort 6: Patients otherwise eligible for Cohorts 1-5 who discontinued another selective RET inhibitor(s) may be eligible with prior Sponsor approval (up to ~50 patients).
- ~~Cohort 7: (up to ~19 patients): Patients with a histologically confirmed stage IB-III A NSCLC and a RET fusion; determined to be medically operable and tumor deemed~~

~~resectable by a thoracic surgical oncologist, without prior systemic treatment for NSCLC. Cohort 7 is described in a separate addendum to this protocol.~~

### 3.6. Phase 2

~~Cohort 7 (up to 19 patients): Patients with a histologically confirmed stage IB-IIIa NSCLC and a RET fusion; determined to be medically operable and tumor deemed resectable by a thoracic surgical oncologist, without prior systemic treatment for NSCLC.~~

#### 4.1. Inclusion Criteria for Phase 1

For patients in Germany: Only adult patients capable of understanding the nature, significance and consequences of the clinical trial and providing informed consent are eligible for participation in the planned clinical trial.

#### 4.2. Inclusion Criteria for Phase 2

~~Cohort 7: Patients with a histologically confirmed stage IB-IIIa NSCLC and a RET fusion; determined to be medically operable and tumor deemed resectable by a thoracic surgical oncologist, without prior systemic treatment for NSCLC. Cohort 7 is described in a separate addendum to this protocol.~~

#### 4.3. Exclusion Criteria for Phase 1 and Phase 2

~~16. Phase 2 Cohort 7 (neoadjuvant treatment): Patient must not have received prior systemic therapy for NSCLC.~~

#### 6.4. Removal of Patients from Therapy or Assessment

- Unacceptable toxicity

**Note:** In Germany, this must be due to > Grade 3 or intolerable Grade 2 adverse event by CTCAE 4.3 considered related to study drug and despite protocol-allowed dose reduction

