### *Hemorrhage*

Rare patients have reported serious hemorrhagic AEs related to study drug. The majority of hemorrhagic events have been Grade 1-2 and non-serious in nature. Clinical signs and symptoms of bruising and bleeding should be monitored while patients are on selpercatinib. For patients who develop an AE  $\geq$  Grade 3, selpercatinib should be held until the event resolves to  $\leq$  Grade 1 (or baseline) and patients with severe or life-threatening hemorrhagic events should discontinue selpercatinib therapy.

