### *Interstitial Lung Disease/Pneumonitis*

For Grade 2, hold dosing until resolution. Resume at next lower dose level. Discontinue selpercatinib for recurrent interstitial lung disease/pneumonitis. For Grade 3 or 4, discontinue selpercatinib.

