### *Chylothorax and Chylous Ascites*

If a patient develops a pleural effusion or abdominal ascites or both while on selpercatinib, fluid sampling and testing should be considered as part of the management algorithm whenever possible. The etiology of this finding varies and distinguishing chylous fluid from malignant (as well as other causes such as infectious) may impact management significantly (for example, presumption of disease progression with premature discontinuation of therapy). Additionally, a diagnosis of chylous effusions or ascites or both may indicate a role for conservative measures such as fluid replacement, dietary alteration, or medical therapy or both (for example, somatostatin analogue) prior to consideration of more invasive measures.

Selpercatinib interruption and dose modification should follow the general strategy based upon severity of the event.

### Phase 1, Cycle 1

Dose reductions are permitted but will be considered a DLT if the dose was reduced for a toxicity(ies) that cannot be reasonably attributed to the patient's underlying disease, other medical condition or concomitant medications.

A patient who experiences a DLT may have selpercatinib dosing held for up to 28 days to allow for recovery (to Grade 1 or less or baseline if baseline is Grade 2 or above).

The patient may restart therapy if it is considered in his/her best interest to continue therapy. Upon restarting, the patient may have the dose reduced by one dose level (Table 6-1). If the patient requires a dose delay of > 28 days, the patient will have treatment permanently discontinued unless there is a compelling clinical rationale for additional dose reduction(s) articulated by the Investigator and approved by the Sponsor. For each patient, a maximum of 2 dose reductions will be allowed, unless there is a compelling clinical rationale for additional dose reduction(s) articulated by the Investigator and approved by the Sponsor.

All dose interruptions and dose modifications and the reasons for those changes will be recorded in the electronic Case Report Form (eCRF).

#### Phase 1 Cycle 2 and Beyond, and Phase 2

A patient who experiences a clinically significant AE (i.e., greater than Grade 2 or more than 1 grade change from baseline if baseline is Grade 2 or above) may have selpercatinib dosing held for up to 28 days to evaluate the AE and to allow for recovery (to Grade 1 or baseline level).

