Upon recovery, the patient may restart therapy if it is considered in his/her best interest to continue therapy. Upon restarting, the patient may have the dose reduced by at least one dose level (Table 6-1). If the AE does not recover to Grade 1 or less within 28 days (or baseline), the patient will have treatment permanently discontinued, unless there is a compelling clinical rationale for additional dose reduction(s) articulated by the Investigator and approved by the Sponsor. For each patient, a maximum of 2 dose reductions will be allowed, unless there is a compelling clinical rationale for additional dose reduction(s) articulated by the Investigator and approved by the Sponsor (Table 6-1).

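### The German note on unacceptable toxicity, as printed, leaves out Grade 3 while admitting intolerable Grade 2 and Grade 4 events

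*Protocol*

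**What the plan says.** Protocol Section 6.4 gives the reasons for removing a patient from treatment. One is unacceptable toxicity, with no grade and no requirement for an earlier dose reduction.

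Appendix K (Germany, item 6.4) adds a note under that reason: "In Germany, this must be due to > Grade 3 or intolerable Grade 2 adverse event by CTCAE 4.3 considered related to study drug". The sentence ends with a second condition: "considered related to study drug and despite protocol-allowed dose reduction". The German change table describes this entry only as "Added note sites in Germany", which does not help to settle the intended threshold.

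Section 6.2.4, which is not among the sections changed for Germany, contains its own stopping instructions:

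- Interstitial lung disease/pneumonitis: "For Grade 3 or 4, discontinue selpercatinib" and "Discontinue selpercatinib for recurrent interstitial lung disease/pneumonitis".
- Hemorrhage: "patients with severe or life-threatening hemorrhagic events should discontinue selpercatinib therapy".
- Phase 1 Cycle 2 and Beyond, and Phase 2: "If the AE does not recover to Grade 1 or less within 28 days (or baseline), the patient will have treatment permanently discontinued", unless the Sponsor approves an exception.

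**The concern.** A stopping threshold should be monotone in severity: if an event of one grade can justify removal, a more severe event of the same kind should too. The printed note breaks this between Grade 2 and Grade 4.

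Sections 3.2.1, 3.3 and 7.9 all send the reader to Section 6.4 for the criteria that end treatment, so the wording there matters. At stake is a clear instruction for a German investigator whose patient has a related Grade 3 event that keeps returning on a reduced dose.

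**Working it through.** No arithmetic applies. The check compares texts.

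**Step 1. Apply the note grade by grade.** Assume the event is drug-related and persists despite an allowed dose reduction, so that only the grade decides.

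| Event | Note as printed (>) | Note with ≥ |
|---|---|---|
| Grade 1 | not met | not met |
| Grade 2, tolerable | not met | not met |
| Grade 2, intolerable | met | met |
| Grade 3 | **not met** | met |
| Grade 4 | met | met |

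Only the Grade 3 row changes. Under the printed symbol, the criterion is met at intolerable Grade 2, lost at Grade 3 and met again at Grade 4.

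**Step 2. Compare with thresholds elsewhere in the protocol.** Section 6.2.4 uses ≥ Grade 3 in four places:

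- Liver function tests: for holding drug, and for discontinuing at 40 mg BID.
- Thrombocytopenia: for holding.
- Hypertension: for discontinuing when it is uncontrolled despite reduction to 40 mg BID.
- Hemorrhage: for holding.

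Its general rule for Phase 1 from Cycle 2 and for Phase 2 begins "A patient who experiences a clinically significant AE (i.e., greater than Grade 2", which also includes Grade 3. Several of these are thresholds for holding rather than for permanent removal, so the parallel is supportive and not exact. The closest matches are the liver and hypertension stops, and both include Grade 3.

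**Step 3. Compare the CTCAE version.** The note says 4.3. Protocol Sections 3.5, 8.5.2 and 9.2 say 4.03, as do the SAP sections on adverse events and on laboratory abnormalities. No other version is cited.

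**Step 4. Ask where the Grade 3 gap could matter.** Many Grade 3 events are caught by Section 6.2.4 anyway: Grade 3 pneumonitis, severe hemorrhage, an event not recovered in 28 days, and the liver and hypertension stops at 40 mg BID. What remains is a related Grade 3 event outside those rules that recovers with each interruption but returns on a reduced dose. Section 6.2.4 normally limits a patient to two reductions, but for that case its general rule does not itself order a stop. The unacceptable-toxicity reason in Section 6.4 would be the natural route, and in Germany it is not met as printed.

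**Step 5. Check whether another text repairs the note.** None was found. Main Section 6.4 sets no grade, and nothing else in the German part of Appendix K returns to the point.

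**The case against.** The strongest objection is that the point rests on one character. The text was read from a PDF, and a ≥ typed as an underlined > may have lost its underline, particularly in an appendix that uses revision marking. A QTcF limit in Table 7-1, footnote j, is visibly garbled, so comparisons in this file are not always clean. This stands as a caution. Against it, ≥ appears correctly throughout Section 6.2.4. The loss can be neither shown nor ruled out, which is why the source should be checked first.

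It is also fair to say that 4.3 for 4.03 is editorial. Section 9.2 fixes the version used for grading, and no grade would change.

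A reader might go further and infer that the note overrides the stops in Section 6.2.4, so that a first Grade 3 or 4 pneumonitis with no earlier reduction would have to stay on drug in Germany. The documents do not support that:

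- Appendix K sets out only changes, and Section 6.2.4 is not listed. Its instructions therefore apply in Germany as written, and none of them depends on meeting the unacceptable-toxicity reason.
- The dose-reduction condition refers to reductions the protocol allows. Where Section 6.2.4 orders an immediate stop, there is no such reduction to try first, so the condition naturally falls away.
- Recurrent pneumonitis is covered by its own instruction. After a first Grade 2 episode, drug is resumed at the next lower dose level, so a recurrence already follows a reduction.

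Other reasons in Section 6.4, such as intercurrent illness, need for alternative treatment and withdrawal of consent, also remain open.

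**Conclusion.** The point holds as an error in the printed threshold, and it is minor. As worded, the German note excludes a related Grade 3 event persisting despite dose reduction while including intolerable Grade 2 and Grade 4 events. No clinical reason for this is given, and ≥ Grade 3 is the likely intent.

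It reaches only German patients for whom stopping for toxicity arises. They are adults only and are not enrolled in Cohorts 2 or 4; the documents do not give their number. No efficacy definition in the SAP depends on whether a stop was classed as unacceptable toxicity, so the efficacy analyses are untouched.

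The conclusion assumes that > is what the source document shows. If the source shows ≥, only the version number needs correcting. The note does not contradict Section 6.2.4 and does not compel continued dosing.

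**What to change.** The sponsor should confirm the intended threshold and check the source file for ≥. If the source does show >, the note in Appendix K (Germany, 6.4) should be changed to: ≥ Grade 3 or intolerable Grade 2 adverse event by CTCAE 4.03, with the rest of the sentence unchanged.

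Optionally, a cross-reference could remind German sites that discontinuations required by Section 6.2.4 apply independently of the note. That is a clarification, not a correction.

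The cost is one phrase in the country appendix at the next amendment, with no new data or procedures.

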## 7. TESTS AND EVALUATIONS

~~Patients who are tolerating selpercatinib may have a reduced in-clinic visit assessment schedule after 6 months on treatment as described in Table 7.1. From Cycle 7 and onward, patients will be required to return to the clinic for in-person visits only during cycles where radiographic disease assessments are required, and for EOT and SFU visits. During non-disease assessment cycles, patients may continue to return for in-person visits or may opt to have routine laboratory tests (e.g., serum chemistries, hematology, and liver function tests) completed at local healthcare facilities in conjunction with a telemedicine visit (telephone or equivalent). During the remote assessment, the site will perform an ECOG assessment, an AE assessment including whether the patient is experiencing any new, or changes to existing, AEs/SAEs and concomitant medications;~~

~~and will confirm study drug compliance and record missed doses. Patient responses during telemedicine visits will be recorded in source documents and results from any local assessments must be provided to the site for data entry into EDC.~~ Patients who are on selpercatinib treatment for at least 2 years will be required to return to the clinic for in-person visits only during cycles where radiographic disease assessments are required, and for EOT and SFU visits. Routine laboratory tests and telemedicine visits are not required but should be performed as clinically indicated during non-disease assessment cycles.

~~Should telemedicine visits result in patient complaint or concern from the study Investigator, the patient should return to the study site or be seen by a local provider for further assessment(s).~~

### Table 7-1: Schedule of Assessments

~~\* For Cycle 7 and beyond, patients may have laboratories (e.g., serum chemistries, hematology, liver function tests, and urinalysis) completed at the study site or at local healthcare facilities during non-disease assessment cycles. As a result of this reduced in-clinic visit assessment schedule, the Sponsor understands that certain assessments (e.g., physical examination, vital signs) may not be obtainable during visits at local healthcare facilities. Beyond Cycle 7, these assessments are optional during local, non-disease assessment cycles, but should be collected when the patient returns to the clinic for disease assessment cycles. Patients who are on selpercatinib treatment for at least 2 years will be required to return to the clinic for in-person visits only during cycles where radiographic disease assessments are required, and for EOT and SFU visits. Routine laboratory tests and telemedicine visits are not required but should be performed as clinically indicated during non-disease assessment cycles.~~

- b. For Cycle 7 and beyond, patients may attend clinic visits only during cycles where radiographic disease assessments are required (Cycle 7, 9, 11, 13, and then Q12W thereafter) if telemedicine visit can be completed along with locally obtained lab assessments. Not applicable for Germany.
- z. Study sites will conduct a telemedicine visit when no in-clinic visit occurs to confirm whether the patient is experiencing any new, or changes to existing, AEs/SAEs and concomitant medications, and to confirm study drug compliance and missed doses. Not applicable for Germany.
- cc. Only for patients with a diagnosis of MTC and diarrhea at baseline. For Cycle 7 and beyond, the patient should personally maintain bowel diary and discuss the diary with the site during ~~telemedicine~~ visits. The bowel diaries should be returned at the next in-clinic visit or provided to study site electronically.

### 8.3 Determination of Sample Size

Notwithstanding the statistical considerations above, if approved by the SRC, enrollment beyond the above sample sizes in each of Cohorts 1-5, will be allowed, in order to accommodate enrollment demand and allow for the characterization of AEs that may occur with low frequency. With a sample size of 150 patients, the probability of observing one or more instances of a specific AE within a cohort with a true incidence rate of 1% and 2% is 77.9% and 95.2%, respectively. With a sample size of 250 patients, the probability of observing one or more instances of a specific AE within a cohort with a true incidence rate of 1% and 2% is increased to 91.9% and 99.4%, respectively. The sample size for Cohort 1 was increased to ~250 to accommodate enrollment demand. Additional enrollment will also allow for the characterization of AEs that may occur with low frequency which would enhance knowledge of the safety profile of selpercatinib. Further, this cohort allows for the enrollment of patients with RET fusion-positive solid tumors other than NSCLC. While the enrollment demand for patients with RET

fusion-positive NSCLC has been adequate for statistical analysis, additional solid tumor types remain underrepresented and enrollment expansion allows for data capture in this population.

## **Appendix L Provisions for Changes in Study Conduct During Exceptional Circumstances**

The changes to procedures described in this appendix are temporary measures intended to be used only during specific time periods as directed by the sponsor in partnership with the investigator. Please note that Appendix L does not apply to Germany and should any of the events described herein requiring mitigation of study procedures be required, these will only be implemented in Germany after approval of a substantial amendment.

### **Denmark**

This section describes protocol changes applicable for participants in study sites in Denmark.

In Denmark, continued access to the investigational medicinal product is not possible as part of the clinical trial. If patients are experiencing clinical benefit with no undue risks at the time of study completion, as determined by the investigator, access to the investigational medicinal product will be provided through permitted alternate approaches if needed.

## **Appendix L      Provisions for Changes in Study Conduct During Exceptional Circumstances**

### **Implementation of this appendix**

The changes to procedures described in this appendix are temporary measures intended to be used only during specific time periods as directed by the sponsor in partnership with the investigator.

### **Exceptional circumstances**

Exceptional circumstances are rare events that may cause disruptions to the conduct of the study. Examples include pandemics or natural disasters. These disruptions may limit the ability of the investigators, participants, or both to attend on-site visits or to conduct planned study procedures.

### **Implementing changes under exceptional circumstances**

In an exceptional circumstance, after receiving the sponsor's written approval, sites may implement changes if permitted by local regulations.

After approval by local Ethical Review Boards, regulatory bodies and any other relevant local authorities, implementation of these exceptional circumstance changes will not typically require additional notification to these groups, unless they have specific requirements in which notification is required (for example, upon implementation and suspension of changes). All approvals and notifications must be retained in the study records.

If the sponsor grants written approval for changes in study conduct, the sponsor will also provide additional written guidance, if needed.

